15.2 Final Report

A final report will be prepared even if the study is prematurely terminated.

15.3 Publication Policy

At the conclusion of the study, a multi-center abstract reporting the results will be prepared and may be presented at a major meeting(s). A multi-center publication may also be prepared for publication in a reputable scientific journal. The publication of results from any single center experience within the study is not allowed until the aggregate study results have been published, unless there is written consent from the study sponsor.

CANDESANT BIOMEDICAL	CLINICAL STUDY PROTOCOL SAHARA STUDY	Document #: CB-CLP-001 Revision: E
----------------------	---	---------------------------------------

APPENDIX A: HDSS

Information and Instructions:**About Sweating:**

Sweating is a natural and healthy part of life. Sweating helps to cool the body and maintain a normal body temperature in a warm environment or during exercise. It is normal to sweat when you are hot, when you are exercising, and when you are feeling stressed.

About Excessive Sweating:

You are in this study because you feel like you sweat too much. You may sweat at times other than when you are warm, exercising, or stressed. The questions below are designed to measure the severity and impact of your excessive underarm sweating during the past week. While you may experience excessive sweating on other parts of your body, these questions are designed to measure the impact of the treatment on your underarm sweating ONLY.

Instructions:

- Please only think about your underarm sweat as you answer these questions.
- Please remember that sweating when you are hot, exercising or stressed is normal, so when you are answering the questions, think about sweating that is beyond normal. For example, you may sweat when you work out at the gym and still answer "never" since sweating at the gym during a strenuous workout is considered to be the body's natural response to keep the body cool.
- There are no right or wrong answers; you should answer truthfully about your excessive underarm sweating experiences during this past week
- If you have any questions, you may contact the study team

The box next to the statement that best describes your feelings about your underarm sweating at the current time should be checked.

Prior to each statement there is a number (1, 2, 3, and 4). This number is the "HDSS score".

HDSS SURVEY		
ASSESSMENT TIME:  Screening  Baseline  1 week  2 weeks  3 weeks  4 weeks  5 weeks  6 weeks  7 weeks  8 weeks  9 weeks  10 weeks  11 weeks  12 weeks  Other	 1.	My underarm sweating is never noticeable and never interferes with my daily activities
	 2.	My underarm sweating is tolerable but sometimes interferes with my daily activities
	 3.	My underarm sweating is barely tolerable and frequently interferes with my daily activities
	 4.	My underarm sweating is intolerable and always interferes with my daily activities

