7.2.1 Inclusion Criteria

The subject must meet all of the criteria listed below at the time of enrollment

Table 1. Inclusion Criteria

I-1	Signed written informed consent, including authorization to release health information. (Subject must be able to read informed consent independently since subjective feedback is required)
I-2	Subject is at least 22 years old at the time of consent
I-3	Female or male, who experiences excessive sweating or has been diagnosed with primary focal hyperhidrosis of the axilla and is in otherwise good general health
I-4	GSP >50mg/5min at room temperature/humidity (20-25.6°C/20-80%) at both screening and baseline
I-5	Subject reports a score of HDSS score of 3 or 4 at both screening and baseline
I-6	Subject agrees to avoid use of topical aluminum compounds, antiperspirants, anticholinergic medications or steroids for the duration of study participation
I-7	Subject is willing and able to follow instructions and likely to complete all requirements for the study, including hair removal requirements
I-8	Women of child-bearing age must have a negative pregnancy test at screening and must be practicing and willing to continue an effective method of birth control from screening visit until study completion.

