8.5.2 Blinding

Subjects in the randomized cohort will be blinded to the Study Arm to which they are randomized.

Site personnel will not be informed of the specific Study Arm assignment (they will only know the treatment # assigned); those administering the treatment will observe the treatment effect and the disposal process and may be unblinded as a result of their observations. This person will not conduct the follow-up assessments. These personnel will be instructed and trained not to reveal the assumed Study Arm assignment to any subject or to any of the other study personnel at the site. Site personnel completing follow-up evaluations will be different from the person who conducted the procedure and, therefore, will be blinded to the subject's treatment.

Subjects will be instructed (by subject handout Appendix G) not to discuss their assumed treatment assignment with anyone at the study site.

Only necessary persons at the sponsor shall know the treatment assignments and only those persons will have access to the database which holds the key for the treatment numbers distributed at each site. All others at the sponsor will remain blinded.

CANDESANT BIOMEDICAL	CLINICAL STUDY PROTOCOL SAHARA STUDY	Document #: CB-CLP-001 Revision: E
---------------------------------	---	---------------------------------------

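### The HDSS and QoL forms describe themselves as measuring the treatment's impact and name 'never' as an example answer, which could cue favourable reporting; the size is unknown and neutral wording removes the cue

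*Protocol*

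**What the plan says.** The introduction to the HDSS form (Protocol, Appendix A) gives two purposes. It first says: "The questions below are designed to measure the severity and impact of your excessive underarm sweating during the past week". The next sentence, which limits the questions to the underarms, says that "these questions are designed to measure the impact of the treatment on your underarm sweating ONLY".

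The instructions contain one worked example. It begins "For example, you may sweat when you work out at the gym and still answer" and then gives the answer 'never'. Only one of the four HDSS options contains that word, option 1: "My underarm sweating is never noticeable and never interferes with my daily activities". The form also carries a neutral instruction: "There are no right or wrong answers; you should answer truthfully about your excessive underarm sweating experiences during this past week".

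The Appendix A form has tick boxes for screening and baseline as well as for each follow-up week. Entry criterion I-5 (Protocol 7.2.1) reads: "Subject reports a score of HDSS score of 3 or 4 at both screening and baseline".

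Appendix C places the same purpose sentence and the same example above the Bother, Impact and QoL-7 questions. Its answer scales run from not at all upward, or are yes/no. It has no counterpart to the reassurance that no answer is right or wrong.

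A self-reported HDSS of 1 or 2 at week 4 is the primary endpoint. Bother and Impact at week 4 are the first two secondaries in the ordered testing (Protocol 9.10.1 and 9.10.2.2; SAP 11.1 and 11.2.2).

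**The concern.** A severity form should ask about severity and leave the inference about treatment to the comparison of arms. Telling subjects that the questions measure what the treatment did invites them to report a change. Before treatment the phrase has nothing to refer to; at week 4 it does. An example that ends in an answer option adds a smaller nudge, because that option counts as a primary success.

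Every between-arm test in the confirmatory sequence rests on these two forms; the third secondary, a two-grade HDSS improvement, also comes from Appendix A. The fourth secondary, gravimetric sweat production, is tested in the active arm alone against zero, and its between-arm comparison is observational. No confirmatory between-arm measure is therefore independent of self-report.

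If subjects in both arms followed such a cue, sham response would rise and the difference would probably narrow. If they followed it differently according to the arm they believed they were in, the comparison would be biased.

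**Working it through.** **The two forms side by side**

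| Feature | Appendix A (HDSS) | Appendix C (Bother, Impact, QoL-7) |
|---|---|---|
| Purpose given as severity and impact of sweating | yes | yes |
| Purpose given as impact of the treatment | yes | yes |
| Pre-treatment time boxes | screening, baseline | baseline |
| Example naming 'never' | yes | yes |
| Options containing 'never' | option 1 only | none |
| Reassurance that no answer is right or wrong | yes | absent |

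The text was evidently not fitted to each form.

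**The plan's sample size (Protocol 9.10.1)**

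Inputs: 85% vs 60% or 73% vs 44%, two-sided 0.05, 80% power. With p̄ the mean of the two rates, the pooled-variance formula is

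n = [1.960·√(2p̄(1−p̄)) + 0.842·√(p_T(1−p_T) + p_S(1−p_S))]² / (p_T − p_S)²

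- 85/60: [1.960·√0.39875 + 0.842·√0.3675]² / 0.0625 = 49 after rounding up; the plan states 50.
- 73/44: [1.960·√0.48555 + 0.842·√0.4435]² / 0.0841 = 45 after rounding up; the plan states 45.

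The stated figures reproduce, the first to within one subject per arm.

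**Illustration of an equal cue**

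Assumption: a share c of subjects who would have scored 3 or 4 tick 1 or 2 instead, in both arms. Then p′ = p + c(1−p), and the difference becomes (1−c)(p_T − p_S). The documents give no value for c, so a range is shown. For example, at c = 10%: 0.85 + 0.1 × 0.15 = 0.865 and 0.60 + 0.1 × 0.40 = 0.640.

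Power is by exact binomial enumeration of the unstratified Mantel-Haenszel test without continuity correction, 50 per arm, counting results that favour the patch.

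| c | 85/60 becomes | Difference | Power | 73/44 becomes | Difference | Power |
|---|---|---|---|---|---|---|
| 0 | 0.850/0.600 | 0.250 | 81.8% | 0.730/0.440 | 0.290 | 85.6% |
| 10% | 0.865/0.640 | 0.225 | 76.0% | 0.757/0.496 | 0.261 | 78.2% |
| 20% | 0.880/0.680 | 0.200 | 69.1% | 0.784/0.552 | 0.232 | 70.1% |
| 30% | 0.895/0.720 | 0.175 | 61.3% | 0.811/0.608 | 0.203 | 61.8% |

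The normal approximation gives the same picture (80.9% to 74.9% and 84.8% to 77.8% at c = 10%). A simulated stratified test with two equal strata and the same response rates in each gave 82.0% for 85/60 with no cue, so ignoring strata matters little here.

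**Sensitivity to the model**

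An equal absolute shift has the opposite effect. Adding 5 points to both arms raises power by the normal approximation from 80.9% to 86.1% (90 vs 65) and from 84.8% to 86.5% (78 vs 49). At 85/60, however, this means converting 0.05/0.15 = 33% of active non-responders but only 0.05/0.40 = 12.5% of sham non-responders, so it is closer to a differential cue than an equal one.

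**Type I error**

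If the true rates are equal and c is the same in both arms, p′ is also equal and the null hypothesis still holds. An equal cue does not create false positives.

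**The case against.** Much of the case on the other side is sound.

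- The sentence about the treatment opens by acknowledging sweating elsewhere on the body. Its evident job is to limit the body site, not to announce benefit. This explains the wording, but the first instruction on the form already limits answers to the underarms, so nothing is lost by changing it.
- Appendix A contains neutral statements too. That stands for HDSS. Appendix C shares the neutral purpose sentence but not the reassurance, so Bother and Impact have less protection.
- The example legitimately tells subjects to disregard normal sweating. Enrolled subjects had to score 3 or 4 at screening and baseline on a form carrying the same text, so the example alone is a weak cause of change by week 4. It points to option 1, not 2, and matches no option in Appendix C. This stands and makes the example the lesser concern. The filter is not complete: Table 5 has site staff administering HDSS before treatment, while follow-up is electronic.
- The planning sham rates of 60% and 44% already allow for substantial sham response, so a cue on top may partly count expectation twice. This is fair, and a reason to treat the power figures as illustration.
- Appendix C is marked as a draft version, and the documents do not show what appears on the electronic screens. This limits certainty, not the value of correcting the text.

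A reader might go further and infer that the wording biases the trial toward the patch. If 10% of non-responders were converted in the active arm only, with no true effect, the chance of a significant result favouring the patch would rise from 2.6% to 6.2% (60% sham rate) or from 2.8% to 8.9% (44%); at 20% it would be 12.9% or 21.7%. The arithmetic is right, but the documents do not tie it to this wording. It assumes that the cue acts in one arm only, although subjects are blinded and told not to discuss their assignment. The statement in Protocol 8.5.2 that "those administering the treatment will observe the treatment effect and the disposal process and may be unblinded as a result of their observations" concerns operators, not subjects. Heat and pain during patch wear could let subjects guess their arm, but that would affect a self-reported endpoint under neutral wording too. These figures describe general unblinding, which rewording would not remove.

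**Conclusion.** The textual fault is certain: both forms misdescribe what they measure, and both name an answer in their only example. That this could cue favourable reporting on the primary endpoint, Bother and Impact is a reasonable inference. That it does so is not shown, and the size is unknown. The phrase about the treatment is the stronger concern.

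The fall to 76% or 78% power rests entirely on an assumed 10% conversion, equal in both arms and proportional to non-responders. It shows mainly that the plan has little power in reserve. Bias would need a response that differs by perceived arm. Neither document plans to ask subjects which arm they think they received, so that possibility could be neither confirmed nor excluded. The point supports an inexpensive correction to the forms, not a claim that the primary test is invalid.

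**What to change.** In Appendices A and C:

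1. Replace the sentence about the impact of the treatment with neutral wording, such as 'Please answer about your underarm sweating only'.
2. Keep the advice to disregard normal sweating during exercise, but delete the closing words of the example that name 'never' as an answer.
3. Add to Appendix C the reassurance that no answer is right or wrong.
4. Use identical text at screening, baseline and every follow-up week, on paper and on screen.

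The HDSS and QoL items, the schedule, the sample size and the analysis stay as they are. The cost is re-approval of the two changed lines, plus the line added to Appendix C. This should be done before first use, since a later change would give subjects different text at baseline and week 4.

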APPENDIX C: QoL SURVEYS

Information and Instructions for Study Subjects:

About Sweating:
Sweating is a natural and healthy part of life. Sweating helps to cool the body and maintain a normal body temperature in a warm environment or during exercise. It is normal to sweat when you are hot, when you are exercising, and when you are feeling stressed.
About Excessive Sweating:
You are in this study because you feel like you sweat too much. You may sweat at times other than when you are warm, exercising, or stressed. The questions below are designed to measure the severity and impact of your excessive underarm sweating during the past week. While you may experience excessive sweating on other parts of your body, these questions are designed to measure the impact of the treatment on your underarm sweating ONLY.
Instructions:

 Please only think about your underarm sweat as you answer these questions. Please remember that sweating when you are hot, exercising or stressed is normal, so when you are answering the questions, think about sweating that is beyond normal. For example, you may sweat when you work out at the gym and still answer "never" since sweating at the gym during a strenuous workout is considered to be the body's natural response to keep the body cool. If you have any questions, you may contact the study team

QUALITY OF LIFE ASSESSMENT QUESTIONS		Version: Draft IDE Submission	
TIME OF ASSESSMENT:  Baseline  1 week  2 weeks  3 weeks  4 weeks  5 weeks  6 weeks  7 weeks  8 weeks  9 weeks  10 weeks  11 weeks  12 weeks  Other	BOTHER: During the past week how bothered were you by your underarm sweating?	 Not at all bothered  A little bothered  Moderately bothered  Very Bothered  Extremely Bothered	

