	IMPACT: During the past week how often did your underarm sweating impact your daily activities?	 Not at all  A little bit  A moderately amount  A great deal  An extreme amount	
	QoL-7: How has your underarm sweating impacted certain areas of your life over the past week? Please indicate Yes or No to the following statements		
	1. I felt embarrassed because of my underarm sweating		 Y  N
	2. I felt frustrated because of my underarm sweating		 Y  N
	3. I felt less confident because of my underarm sweating		 Y  N
	4. I had to change my shirt during the day because of my underarm sweating		 Y  N
	5. I had to take more than 1 shower or bath a day because of my underarm sweating		 Y  N
	6. My underarm sweating kept me from doing an activity that I wanted or needed to do		 Y  N
7. I wanted to avoid interactions with other people because of my underarm sweating		 Y  N	

CANDESANT BIOMEDICAL	CLINICAL STUDY PROTOCOL SAHARA STUDY	Document #: CB-CLP-001 Revision: E
-------------------------	---	---------------------------------------

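### The HDSS form sets two reference periods for the item behind the primary endpoint: the past week in its instructions, the current time at the tick-boxes

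*Protocol*

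**What the plan says.** Appendix A of the protocol contains the HDSS form and its instructions.

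- **Introduction:** the questions are "designed to measure the severity and impact of your excessive underarm sweating during the past week".
- **Instruction bullet:** "you should answer truthfully about your excessive underarm sweating experiences during this past week".
- **Sentence above the boxes:** the box for the statement "that best describes your feelings about your underarm sweating at the current time should be checked".
- **Response options:** present tense with no period stated; grade 3, for example, reads "My underarm sweating is barely tolerable and frequently interferes with my daily activities".

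Protocol section 6.2 makes HDSS 1 or 2 at 4 weeks the primary endpoint and refers to Appendix A for scoring. Sections 8.2 and 8.3.1 have the scale explained according to sponsor training and Appendix A. They stress that it concerns the underarms and do not mention a period. SAP sections 5 and 11.1 define success and the endpoint without a recall period.

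The two quality-of-life items in Appendix C carry the period in the question itself: "During the past week how bothered were you by your underarm sweating" and "During the past week how often did your underarm sweating impact your daily activities".

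**The concern.** A subject who follows the introduction rates the week. A subject who follows the sentence next to the boxes rates the present. Someone whose sweating varies may give grade 3 on one reading and grade 2 on the other, and that is the cut that defines a responder.

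The same item fixes eligibility (criterion I-5), the randomization and CMH strata, secondary endpoint 3, duration of efficacy and entry to extended follow-up. The setting also changes. Table 5 lists site-administered HDSS separately from the weekly electronic follow-up, and Table 4 allows either a visit or an electronic response. What counts as the current time can therefore differ between baseline and week 4.

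What is at stake is precision at the primary endpoint, in a trial planned for about 80% power in the scenario that set its size.

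**Working it through.** **1. Text comparison.** Appendix A names the past week twice and the current time once. The options name neither. Protocol sections 6.2, 8.2 and 8.3.1 and SAP sections 5 and 11.1 name no period. The conflict is in current text and is not resolved elsewhere.

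**2. The plan's own sample size.** Inputs from protocol 9.10.1 and SAP 11.1: 85% vs 60% needs 50 per arm and 73% vs 44% needs 45 per arm, at 80% power and two-sided 0.05. The pooled-variance formula is

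n = [1.960·√(2p̄(1−p̄)) + 0.842·√(p₁(1−p₁) + p₂(1−p₂))]² / (p₁−p₂)²

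- 85% vs 60%: p̄ = 0.725; (1.238 + 0.510)² / 0.0625 = 48.9, so 49 (stated 50).
- 73% vs 44%: p̄ = 0.585; (1.366 + 0.560)² / 0.0841 = 44.1, so 45 (stated 45).

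The stated sizes are reproduced closely enough.

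**3. Power at 50 per arm without misclassification.** All outcomes of two binomials with n = 50 were enumerated, rejecting when |Z| > 1.96, with

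Z = (X − m/2) / √(m(100−m)/(4·99))

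Here X is the number of responders in the treated arm and m the number in both arms. Power is 81.8% (85% vs 60%) and 85.6% (73% vs 44%). The normal approximation gives 80.9% and 84.8%. One stratum is used because the documents do not give the split between HDSS 3 and 4.

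**4. Illustration with an assumed misclassification share e.** The documents give no rate, so e = 2.5%, 5% and 10% are assumptions. Two patterns were run, identical in both arms:

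- Answers move only from 3 to 2: p′ = p + (1−p)e. The difference shrinks by the factor 1−e.
- Answers cross in both directions: p′ = p(1−e) + (1−p)e. The difference shrinks by the factor 1−2e.

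| Scenario | e | 3 to 2 only: rates | Power | Both directions: rates | Power |
|---|---|---|---|---|---|
| 85 vs 60 | 2.5% | 85.4 vs 61.0 | 80.5% | 83.3 vs 59.5 | 76.4% |
| | 5% | 85.8 vs 62.0 | 79.1% | 81.5 vs 59.0 | 70.4% |
| | 10% | 86.5 vs 64.0 | 76.0% | 78.0 vs 58.0 | 57.7% |
| 73 vs 44 | 2.5% | 73.7 vs 45.4 | 83.9% | 71.9 vs 44.3 | 81.7% |
| | 5% | 74.4 vs 46.8 | 82.1% | 70.7 vs 44.6 | 77.3% |
| | 10% | 75.7 vs 49.6 | 78.2% | 68.4 vs 45.2 | 67.1% |

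Movement only from 2 to 3 falls between the two patterns. For 85% vs 60% it gives 77.9%, 73.9% and 66.3%.

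**5. Type I error.** Under either formula, equal true rates stay equal after misclassification. Non-differential error therefore does not create a false difference.

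**The case against.** The best reply is that few subjects would take the current-time reading. The past week appears twice, once as a direct instruction. The outlying sentence is passive and sits beside the note on how the score is numbered. The options ask how often sweating interferes with daily activities, which needs a span of time. In a form repeated weekly, the current time may simply mean now as opposed to before treatment. Staff explain the scale at screening and baseline. This stands as a limit on how often the conflict matters, but it does not remove an explicit instruction placed right above the boxes.

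The figures are also open to challenge. A rested subject in a cool clinic would tend to drift towards a lower grade, so the one-way columns describe that mechanism and the two-way columns are a worst case. The planning rates come from company and published trials and may already contain ordinary reporting error, so adding more could double count. Both points stand. So does a third: the electronic screen is not in the documents and may be worded differently.

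A reader might infer that the wording biases the result towards the device. The documents do not support that: both arms get the same form and subjects are blinded (protocol 8.5.2). A reader might also take the fall to 58% as the expected loss. It rests on the highest assumed rate and the least favourable pattern, and nothing in the documents supports either.

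**Conclusion.** The contradiction is real and unresolved, in the form behind the primary endpoint. Its expected effect is dilution of the treatment difference, by an unknown amount. It does not threaten the validity of a positive result.

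Under the one-way pattern and the assumed rates, the power loss is about 1 to 6 points for 85% vs 60% and 2 to 7 points for 73% vs 44%. The two-way worst case loses up to 24 and 19 points. These figures assume 50 evaluable subjects per arm, true rates equal to the planning rates, a single stratum and equal misclassification in both arms. The case for the change is that it is cheap and removes a source of noise; it is not that a known loss has been shown.

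A separate, minor point: the Impact item (secondary endpoint 2) asks "how often did your underarm sweating impact your daily activities" but its options are amounts. That is not a recall-period conflict and no size can be attached to it.

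**What to change.** Before first use, change the tick-box sentence in Appendix A so that it refers to the past week. Use the same sentence on the paper and electronic HDSS forms, so that screening, baseline and every follow-up score share one period, as the Bother and Impact items already do. Repeat the period in the endpoint definitions in protocol 6.2 and SAP 11.1.

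If enrolment has begun, do not switch everyone on one date: some subjects would then have baseline and week 4 scored on different versions, which would disturb the two-grade endpoint. Keep each subject on one version at least from baseline to week 4, and record the version.

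Separately, reword the Impact stem to match its options.

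The cost is a form revision with no new data collection. It is more than a notification: protocol 12.4 requires IRB approval of amendments, and 12.5 requires submission to FDA and the IRBs, with any necessary approvals in writing before the change is made.

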6.2 Primary Efficacy Endpoint

Proportion of subjects in the randomized cohort with Hyperhidrosis Disease Severity Scale (HDSS) of 1 or 2 at the 4-weeks follow-up visit by treatment group. HDSS Scoring is shown in **Appendix A**.

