7.2.2 Exclusion Criteria

If any of the following criteria exist, the subject is not eligible for participation in the study.

Table 2. Exclusion Criteria

ELIGIBILITY: EXCLUSION CRITERIA	
E-1	Active skin disease, irritation, or abrasions at either axilla based on physical examination by physician at baseline.
E-2	Subject's medical history is indicative of secondary or diffuse hyperhidrosis and/or subject has a diagnosis of secondary or diffuse hyperhidrosis
E-3	GSP exceeds 300 mg/5 min in either axilla at either screening or baseline
E-4	GSP readings differ by more than 100% in either axilla between screening and baseline.
E-5	Hair bearing area of the axillae is more than 6 in length and/or 2.75 in width or is not able to be fully covered by the active (foil) area of one study patch
E-6	Treatment with botulinum toxin for excessive sweating or hyperhidrosis within 1 year
E-7	Undergone any procedures, including for hyperhidrosis, which may affect the axillary areas (e.g., laser hair removal within the last 3 months; or Skoog procedure, any type of sympathectomy, gland excision, or other surgery; thermolysis, liposuction; or iontophoresis) or is planning to undergo any of these procedures during the course of the study
E-8	Use of prescription, prescription strength, or clinical strength topical aluminum compounds for axillary hyperhidrosis (e.g., Maxim, Drysol, Certain Dri) for 30 days prior to screening
E-9	Use of over-the-counter antiperspirants and antiperspirant deodorants for 2 days prior to screening
E-10	Concurrent use of anticholinergic medications (including Qbrexza, glycopyrronium, glycopyrrolate, clonidine, atropine, Bellargal-S), beta blockers, calcium channel blockers, or other topical or systemic treatments that may affect hyperhidrosis symptoms starting at screening visit
E-11	Use of a topical steroid on either of the treatment areas (e.g., hydrocortisone, triamcinolone) within 14 days prior to screening
E-12	Presence of a psychological disorder which may interfere with perception of self or perception of severity of sweating
E-13	Use of neuromodulator (e.g. Botox, Dysport, Xeomin) to the hands in the prior 12 months
E-14	Patients with unevaluated lymphadenitis or enlarged lymph nodes should also not be enrolled in case the lymph nodes are reactive or potentially indicative of cancer
E-15	Subjects with allergy to any of the ingredients of the patch

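### Appendix A gives the HDSS two recall periods, the past week and the current time; neither document says which governs, so a score near the 2/3 cut can depend on the line followed.

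*Protocol*

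**What the plan says.** Protocol Appendix A states the time frame three times. The introduction says that the questions are "designed to measure the severity and impact of your excessive underarm sweating during the past week". The third instruction tells the subject that "you should answer truthfully about your excessive underarm sweating experiences during this past week". The line on marking the form then asks for the statement that best "describes your feelings about your underarm sweating at the current time should be checked".

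The four answers name no period. Answer 2, the upper limit of response, reads "My underarm sweating is tolerable but sometimes interferes with my daily activities". In Appendix C, by contrast, the Bother, Impact and QoL-7 items carry their own period; the Bother item begins "During the past week how bothered were you by your underarm sweating".

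The Protocol relies on this form. Section 6.2 defines the primary endpoint as HDSS 1 or 2 at 4 weeks and adds "HDSS Scoring is shown in Appendix A". Sections 8.2 and 8.3.1 refer to Appendix A for explaining the scale at screening and baseline. Criterion I-5 requires that "Subject reports a score of HDSS score of 3 or 4 at both screening and baseline". SAP section 11.1 repeats the endpoint and names no recall period.

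**The concern.** A single self-reported item carries most of the efficacy analysis. The 2/3 cut sets entry (I-5), primary response (Protocol 9.10.1, SAP 11.1) and the reversion event in the duration analysis (SAP 11.3.4). The 3/4 cut sets the randomization stratum and the CMH stratum. The change in score sets the third secondary endpoint. With two time frames on the form, two subjects with the same history can give different scores, and one subject can answer differently at different visits.

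The mode of administration adds a route for this. Table 5 lists HDSS by site at screening and baseline and electronically during follow-up. If the two modes stress different lines, the baseline and week-4 scores could refer to different periods.

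What is at stake is measurement noise in a dichotomised primary outcome, in a trial planned with little spare power.

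**Working it through.** **1. The wording side by side (Appendix A)**

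| Place on the form | Time frame |
|---|---|
| Introduction | past week |
| Third instruction | past week |
| Line on which box to mark | current time |
| Four answers | none stated; frequency words (never, sometimes, frequently, always) |

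Two of the three statements agree, and frequency words need a period. Both facts suggest that the past week was intended. But the line that differs is the one telling the subject how to choose the box, and nothing on the form ranks the lines.

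**2. Who can be affected**

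For the primary endpoint, a subject is affected only if the past-week answer and the current-time answer fall on opposite sides of 2/3. Even then, nothing is misclassified unless subjects follow different lines. Take one line as the reference. With d the share of subjects who are discordant across the cut, and s the share of those who follow the other line, the flip rate is m = d × s. If everyone follows the same line, m = 0. If half follow each line (s = 0.5), m = 2% needs d = 4% and m = 5% needs d = 10%. The documents give neither d nor s.

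**3. Reproducing the planned sample size (Protocol 9.10.1, SAP 11.1)**

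Inputs: 85% vs 60% and 73% vs 44%, two-sided 0.05, 80% power, 1:1 allocation.

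Formula: n per arm = [1.960 × √(2p̄(1−p̄)) + 0.842 × √(p₁(1−p₁) + p₂(1−p₂))]² / (p₁−p₂)², where p̄ is the mean of p₁ and p₂.

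- 85% vs 60%: p̄ = 0.725; [1.960 × √0.39875 + 0.842 × √0.3675]² / 0.0625 = 48.9, so 49 (stated 50).
- 73% vs 44%: p̄ = 0.585; [1.960 × √0.48555 + 0.842 × √0.4435]² / 0.0841 = 44.1, so 45 (stated 45).

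The plan's figures reproduce. At 50 per arm, power = Φ{[(p₁−p₂)√50 − 1.960√(2p̄(1−p̄))] / √(p₁(1−p₁) + p₂(1−p₂))}, which gives 80.9% for 85% vs 60% and 84.8% for 73% vs 44%.

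**4. Illustration of the power loss**

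Assumption, not taken from the documents: responder status is flipped at random at rate m, equally in both arms and both directions. The observed rate is p(1−m) + (1−p)m, so the difference shrinks by the factor (1−2m). For example, at m = 5%, 0.85 becomes 0.85 × 0.95 + 0.15 × 0.05 = 0.815, and 0.60 becomes 0.60 × 0.95 + 0.40 × 0.05 = 0.590.

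| m | 85% vs 60% becomes | Power, 50 per arm | 73% vs 44% becomes | Power, 50 per arm |
|---|---|---|---|---|
| 0 | 85.0 vs 60.0 | 80.9% | 73.0 vs 44.0 | 84.8% |
| 2% | 83.6 vs 59.6 | 76.7% | 72.1 vs 44.2 | 81.6% |
| 5% | 81.5 vs 59.0 | 69.7% | 70.7 vs 44.6 | 76.0% |

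In the scenario that sets the sample size, 2% is enough to go below the planned 80%. In the other, 2% is not but 5% is.

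**The case against.** Several points on the other side are sound.

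- **The intended reading is fairly clear.** Two lines, the frequency wording, the weekly surveys and Appendix C all point to the past week. This stands. It makes the correction uncontroversial, but it does not tell a subject which line to obey.
- **Frequent disagreement at week 4 is not shown.** Treatment is given once, and Protocol section 4.3 expects the effect to last 6-8 weeks on average. At week 4 both time frames lie after treatment and within that period. This stands: responder status can depend on the line followed, and for many subjects it may not.
- **The flip rate has no source.** This stands. The planning rates also come from earlier trials whose HDSS wording is not shown, so they may already contain some recall noise.
- **Training may settle the matter.** Staff explain the scale using sponsor instructions and training. Neither the training material nor the electronic screen text is in the documents, so this may help but cannot be credited.
- **The duration analysis is little affected.** It is observational and scored weekly, so a shift of up to 7 days is about one step.

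A reader might also take exclusion E-9, "Use of over-the-counter antiperspirants and antiperspirant deodorants for 2 days prior to screening", as proof that the two readings diverge. It does not show this for the primary endpoint. At screening, a past-week answer can cover 7 − 2 = 5 days of permitted use. If baseline follows about 72 hours later (Appendix D), at most 7 − 2 − 3 = 2 such days remain, and none remain once the gap is 5 days or more. By week 4, I-6 and section 8.7.5 have barred antiperspirants throughout, so either reading covers a period without them. E-9 bears on the entry score only.

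**Conclusion.** The contradiction is real, stands in the current text, and is not resolved in either document. Because it sits in the instrument for the primary endpoint, it should be corrected, although its effect may be small.

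The supported conclusion is limited. Subjects near a cut can be classed differently depending on the line they follow. With the same form in both arms, the expected result is non-differential misclassification and some loss of power. A reader might infer bias between arms or an inflated type I error. The documents support neither: if the true response rates are equal and both arms share one flip rate, the observed rates are equal too.

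The size is unknown. The figures of about 77% and 70% power (from about 81%, at 85% vs 60%) rest on assumed random flip rates of 2% and 5%, equal in both arms, with 50 evaluable subjects per arm. They show how little slack the plan has and are not an estimate of the loss.

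**What to change.** Use one recall period at every administration. In Appendix A, change the box-marking line to refer to the past week instead of the current time. This matches the rest of that form and Appendix C, and it suits a weekly survey, since each answer then covers the interval since the last one. Put the identical sentence in the site-administered version (screening and baseline) and the electronic version (follow-up), and state the recall period in the endpoint definitions in Protocol 6.2 and SAP 11.1.

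Cost: one sentence on the form and a change to the electronic survey text, with no extra visits or subjects. It has to follow the amendment route in Protocol 12.4 and 12.5, with submission to FDA and IRB approval; notification alone is not enough. Forms already completed under the mixed wording should be flagged so that their number by arm and visit can be reported.

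Downside: a past-week answer at screening can still include antiperspirant days that E-9 permits. The change of wording does not remove that overlap, and the amendment should acknowledge it.
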